## 4. Sample size calculation

In a previously published study conducted at our institution, the incidence of postoperative prolonged ileal obstruction (PPOI) was approximately 38.0% (1), a figure we approximated to be equivalent to the incidence of postoperative gastric dysfunction (POGD). The ratio of the POGD group to the non-POGD group was approximately 3:5. Sample sizes were determined based on the primary study endpoints, and the mean lactate dehydrogenase (LDH) in the POGD group on postoperative day 1 (POD.1) was  $(1406.5 \pm 70)$ , as per the pretest results. The mean LDH for the non-POGD group was  $1210 \pm 343$ . Utilizing a one-sided, two-sample unequal-variance t-test with a power of 0.8 and an  $\alpha$ -value of 0.05, calculated using PASS2021 (NCSS, USA), the required number of cases was determined to be 45. The Neutrophil-to-Lymphocyte Ratio (NLR) value for the POD.1 POGD group was  $(156.3 \pm 14.7)$ , while the mean NLR value for the non-POGD group was  $(39.4 \pm 37.5)$ . The calculated sample size for this comparison was 8 cases, with a maximum sample size of 45 cases. In this study, age and TNM stage were primarily controlled as confounders. Assuming that 5 event samples are required to control for each variable, an additional sample of 14 cases is necessary,

bringing the total required sample size to 59 cases. Considering a 5% dropout rate, the final recruitment requirement is 63 cases.

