## **5. Statistical analysis**

Statistical analyses were performed by SPSS statistical software v.17.0 (SPSS Inc., Chicago, IL, USA) and R Language v.4.0.3 (R Foundation for Statistical Computing, Vienna, Austria). Measures that met normality were expressed as mean  $\pm$  standard deviation were analyzed using the t-test, and measures that did not meet normality were expressed as median and interquartile range and analyzed using the Mann-Whitney rank sum test. The cutoff value was selected by the use of the Youden index (sensitivity + specificity - 1), and the count data were expressed as number of cases and percentages and analyzed using chi-square test. Predictors of postoperative complications and POGD were studied by univariate and multivariate logistic regression (LR). The diagnostic performance of biomarkers was assessed by receiver operator curve (ROC) analysis.

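### If the SAP's pilot NLR figures hold, the age- and TNM-adjusted logistic regression has a substantial chance of separation (about 40–90%, depending on the shape of NLR), and SAP section 5 has no rule for it

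*SAP*

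**What the plan says.** The regression is planned in SAP section 5: "Predictors of postoperative complications and POGD were studied by univariate and multivariate logistic regression (LR"). The software is SPSS 17.0 and R 4.0.3. The section does not name an estimation method, choose between Wald and likelihood-ratio p-values, or say what happens if a model has no finite estimate. It does not list covariates either. Those come from SAP section 4: "In this study, age and TNM stage were primarily controlled as confounders".

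Section 4 also supplies the expected data:

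- NLR with POGD: "value for the POD.1 POGD group was $(156.3 \pm 14.7").
- NLR without POGD: "while the mean NLR value for the non-POGD group was $(39.4 \pm 37.5").
- NLR sample size: "The calculated sample size for this comparison was 8 cases".
- LDH with POGD: "on postoperative day 1 (POD.1) was $(1406.5 \pm 70)$ , as per the pretest results".
- LDH without POGD: "The mean LDH for the non-POGD group was $1210 \pm 343".
- Event rate: "the incidence of postoperative prolonged ileal obstruction (PPOI) was approximately 38.0" percent, taken as the POGD rate, with a group ratio of about 3:5.
- Total: 59 patients, recruited as 63 after a 5% dropout allowance.

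Protocol section 2 makes day-1 drain-fluid LDH and NLR the primary markers. Its secondary objective 4 combines peritoneal and blood markers to predict POGD. SAP section 5 also plans a t-test or Mann-Whitney test, a Youden cut-off and ROC analysis. As written, none of these adjusts for age or TNM stage.

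**The concern.** The pilot NLR means lie far apart relative to their spread. When a marker, alone or with covariates, divides events from non-events without overlap, ordinary logistic regression has no finite maximum-likelihood estimate. Software stops at a very large odds ratio with a huge standard error, sometimes with a warning. The Wald p-value that standard coefficient tables print then becomes non-significant because the association is so strong.

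At stake is the adjusted result for a primary marker. Logistic regression is the only planned analysis that can control for the two confounders named in SAP section 4. A rescue method chosen after separation has been seen would be a data-driven choice.

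**Working it through.** **Inputs (SAP section 4).** NLR 156.3 ± 14.7 versus 39.4 ± 37.5, with ± read as SD. N = 59 at 3:5: 59 × 3/8 = 22.1, so 22 versus 37. N = 63: 63 × 3/8 = 23.6, so 24 versus 39.

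**The plan's own NLR figure.** Welch t-test, one-sided α = 0.05, difference 156.3 − 39.4 = 116.9. With 3 + 5 patients, SE = √(14.7²/3 + 37.5²/5) = √(72.0 + 281.3) = 18.8, and 116.9/18.8 = 6.2. Power exceeds 0.99. Even 2 + 4 gives 0.997, and 3 + 5 = 8 is the smallest exact 3:5 split. The stated 8 therefore fits these inputs read as SDs. The dropout step also reproduces: 59/0.95 = 62.1, rounded up to 63.

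**Discrimination implied.** Under normality, AUC = Φ(116.9/√(14.7² + 37.5²)) = Φ(116.9/40.28) = Φ(2.90) = 0.998.

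**NLR alone.** Complete separation means that the lowest POGD value exceeds the highest non-POGD value:

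P = ∫ n₁ f₁(t) [1 − F₁(t)]^(n₁−1) F₀(t)^(n₀) dt,

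where subscript 1 is POGD and 0 is non-POGD. With normal shapes this is 0.701 at 22/37 and 0.679 at 24/39. With a gamma or lognormal non-POGD group of the same mean and SD, it is 0.28 or 0.32 at 22/37.

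**With covariates.** These are simulations at 22/37 with a linear-programming check for separation. Age and TNM stage were taken as unrelated to POGD, and NLR and LDH as independent within group. Ranges cover separate runs and TNM codings.

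| Model | Normal NLR | Skewed non-POGD NLR |
|---|---|---|
| NLR alone | 70% | 28–32% |
| NLR + age + TNM | 86–90% | 40–45% |
| NLR + LDH + age + TNM | 95–97% | 62–63% |
| NLR cut at Youden index: zero cell | 99.5% | 98–99% |

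**P-values, NLR-only model at 22/37.** Wald p exceeded 0.05 in every separated sample and in some of the others:

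- Normal: 0.702 + 0.298 × 0.519 = 0.857, so 86% of all samples.
- Gamma: 0.274 + 0.726 × 0.173 = 0.400, so 40% of all samples.

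The likelihood-ratio p was below 0.001 in essentially all samples. For the age- and TNM-adjusted model, a smaller simulation (300–600 trials per scenario) found Wald p < 0.05 in 6% (normal) or 46% (gamma). The Firth penalised likelihood-ratio test was significant in all of the same samples.

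**Sensitivity to the pilot contrast (NLR alone, 22/37, one input changed at a time).**

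| POGD mean ± SD | Normal | Skewed |
|---|---|---|
| 156.3 ± 14.7 (SAP) | 70% | 28–32% |
| 156.3 ± 25 | 33% | 13–17% |
| 156.3 ± 37.5 | 9% | 4–6% |
| 125 ± 14.7 | 12% | 5–9% |

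In the last row the AUC under normality is still 0.98.

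**The case against.** A reader might infer that the model will usually separate and that the best marker will therefore be reported as non-significant with an infinite odds ratio. The documents do not support that reading, for four reasons.

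- **Shape.** NLR cannot be negative, yet a normal distribution with 39.4 ± 37.5 puts Φ(−39.4/37.5) = 14.7% of non-POGD values below zero, about 5 of 37. SAP section 4 sizes on a t-test, and section 5 keeps mean ± SD for normal measures, so normality is the plan's working assumption but not a plausible fit. With skew, separation of the age- and TNM-adjusted model is a minority outcome. It becomes a majority only if LDH is added or NLR is dichotomised, and section 5 specifies neither.
- **Pilot values.** No pilot size is given. The sensitivity table shows that modest optimism in the POGD mean or SD removes most of the risk for NLR alone.
- **Test.** Section 5 names neither maximum likelihood nor the Wald test. Maximum likelihood is inferred from unqualified logistic regression, and non-significance is specific to Wald. Software would print a very large finite odds ratio or a warning.
- **Other analyses.** The t-test or Mann-Whitney and ROC results would show NLR as strongly associated in the same sample, so the report as a whole would not miss it.

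All four points stand, and they limit the size of the claim. They do not remove it. A failure chance of about 40% under the milder shape, in the only adjusted analysis and on the plan's own inputs, still needs a rule set in advance.

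**Conclusion.** The concern holds as a conditional one. If the pilot NLR values hold at about 22 versus 37 patients, the adjusted model has a substantial chance of no finite ordinary estimate: about 86–90% under normality and 40–45% under right skew. Adding LDH raises this to about 60–97%, depending on shape. A Youden-dichotomised NLR gives a zero cell in about 98% or more.

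The consequence is an unusable odds ratio and a misleading default p-value in the regression table. It does not mean that the association goes undetected.

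The figures assume that ± is an SD, that age and TNM stage are unrelated to POGD, and that NLR and LDH are independent within group. This should be fixed before analysis. Confidence is moderate, because the size depends on the shape of NLR and on pilot figures that may be optimistic.

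**What to change.** In SAP section 5, state that the POGD logistic models for NLR and LDH use Firth penalised likelihood, with penalised likelihood-ratio p-values and profile-likelihood confidence intervals, fitted in R. Report the age- and TNM-adjusted effect of each primary marker from its own model. Keep a combined-marker model for Protocol secondary objective 4, also fitted with Firth. Using separate models alone would leave that objective unanswered.

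The cost is a few SAP sentences and a different R function. No extra patients or data are needed, and R is already listed. There are two downsides. Odds ratios are shrunk slightly towards 1. Predicted probabilities are pulled towards 0.5, so an intercept correction is needed if predicted probabilities are reported.

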2. The study aims to explore the correlation between albumin, adenosine deaminase (ADA), lymphocyte-monocyte ratio (LMR), prognostic nutritional index (PNI) and other inflammation indicators in drainage fluids on day 1 and day 3 following colorectal cancer surgery, and the occurrence of POGD.

3. The study aims to explore the correlation between neutrophil-lymphocyte ratio (NLR), lymphocyte-monocyte ratio (LMR), platelet-lymphocyte ratio (PLR), systemic immune-inflammatory index (SII), and other inflammation indicators in peripheral blood on day 1 and day 3 following colorectal cancer surgery, and the occurrence of POGD.

4. Combined inflammatory markers in peritoneal fluid and peripheral blood to predict POGD.

5. To evaluate the practical application of the I-FEED score in clinical practice.

3. Study endpoints

Primary endpoint:

Grading of postoperative gastrointestinal function (according to the scoring system based on intake, sensation of nausea, vomiting, physical examination, and duration of symptoms (I-FEED). normal (0-2), postoperative gastrointestinal intolerance (POGI) (3-5), and postoperative gastrointestinal dysfunction (POGD) (>6).

Secondary endpoints:

- a. Time to first postoperative deflation.
- b. Time to first postoperative bowel movement.
- c. Time to first postoperative food tolerance.
- d. Morbidity and mortality from 30-day postoperative complications .

4. Outcome Measures

Primary Outcome Measure:

Measurement of drainage fluid lactate dehydrogenase (LDH) and neutrophil to lymphocyte ratio (NLR) on postoperative day 1

Secondary Outcome Measure :

- a. Measurement of drainage fluid LDH and neutrophil to lymphocyte ratio (NLR) on postoperative day 3.
- b. Measurement of drainage fluid albumin, adenosine deaminase (ADA), lymphocyte-monocyte ratio (LMR), prognostic nutritional index (PNI) on postoperative day 1.
- c. Measurement of drainage fluid albumin, adenosine deaminase (ADA), lymphocyte-monocyte ratio (LMR), prognostic nutritional index (PNI) on postoperative day 3
- d. Measurement of blood serum neutrophil-lymphocyte ratio (NLR), lymphocyte-monocyte ratio (LMR), platelet-lymphocyte ratio (PLR), systemic immune-inflammatory index (SII) on postoperative day 1.
- e. Measurement of blood serum neutrophil-lymphocyte ratio (NLR), lymphocyte-monocyte ratio (LMR), platelet-lymphocyte ratio (PLR), systemic immune-inflammatory index (SII) on postoperative day 3.

4.Sample collection

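### SAP 5 does not limit the terms in the POGD regressions or force in age and TNM, although about 22 events support only about 4 variables against 20 named marker-days

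*SAP*

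**What the plan says.** SAP section 5 gives the regression plan in one sentence: "Predictors of postoperative complications and POGD were studied by univariate and multivariate logistic regression (LR". The section closes with "The diagnostic performance of biomarkers was assessed by receiver operator curve (ROC) analysis". It states no candidate list, entry threshold, limit on terms, forced covariates or correction for optimism.

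SAP section 4 names age and TNM stage as the confounders to be controlled and adds 14 cases for them: "Assuming that 5 event samples are required to control for each variable". The total is 59 evaluable patients, 63 recruited. On the event fraction it says "The ratio of the POGD group to the non-POGD group was approximately 3:5".

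Protocol section 4 (Outcome Measures) lists six drain markers (LDH, NLR, albumin, ADA, LMR, PNI) and four blood markers (NLR, LMR, PLR, SII), each on POD1 and POD3. Protocol section 2 leaves the list open. Secondary objective 3, for example, ends its blood markers with "and other inflammation indicators in peripheral blood on day 1 and day 3", and objective 2 has a similar phrase for drain fluid. Secondary objective 4 reads: "Combined inflammatory markers in peritoneal fluid and peripheral blood to predict POGD".

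**The concern.** SAP section 4 counts events for age and TNM only. The protocol then offers many more variables to the regression, and SAP section 5 does not say how many may enter or how they are chosen. That unstated choice decides whether the 5-events rule is kept.

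Three results are at stake:

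- **The adjusted predictors.** If markers are picked on their univariate p-values, some will be picked by chance.
- **The combined model of objective 4.** Its AUC, computed on the data that built it, will look better than it is.
- **The confounder adjustment.** SAP section 5 does not name age or TNM, so nothing carries the adjustment of SAP section 4 into the fitted models. A later check of accuracy would not restore a confounder that had been left out.

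**Working it through.** **The plan's own figures.** SAP section 4: 45 + 14 = 59, and 59 / 0.95 = 62.1, rounded up to 63, as stated. The 14 extra cases match 5 events for one variable (5 / 0.375 = 13.3, rounded up to 14). Two variables would need 10 / 0.375 = 26.7, so 27. That is a separate matter, but it shows how little of the sample was budgeted for model terms.

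**Events available.** A 3:5 ratio is 37.5% events: 59 × 0.375 = 22.1 (22.4 at 38%). All 63 recruits would give 63 × 0.375 = 23.6. At 5 events per variable, 22.1 / 5 = 4.4, so 4 variables.

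**Candidates.** 6 drain markers × 2 days + 4 blood markers × 2 days = 20. Events per candidate: 22.1 / 20 = 1.1. Applied to all 20, the rule needs 100 events, or 100 / 0.375 = 267 patients (264 at 38%).

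**A model that fits.** Marker + age + TNM as one term is 3 parameters and needs 15 events, within 22. The coding of TNM matters. As a three-level factor it takes 2 parameters (4 in all, 20 events). As a four-level factor it takes 3 (5 in all, 25 events), which is too many.

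**AUC implied by the planning figures.** For normal markers, AUC = Φ(difference / √(SD₁² + SD₂²)).

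- LDH: Φ((1406.5 − 1210) / √(70² + 343²)) = Φ(196.5 / 350.1) = 0.713.
- NLR: Φ((156.3 − 39.4) / √(14.7² + 37.5²)) = Φ(116.9 / 40.3) = 0.998.

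**Null scenarios.** I simulated 22 events, 37 non-events and 20 normal markers unrelated to POGD. Markers passing a univariate logistic screen at p<0.05 went into a multivariable model, and its apparent AUC was recorded. The threshold and the correlations are my assumptions. Ranges cover repeated runs, and Wald tests give the lower ends of the first results column. For independent markers the formula 1 − 0.95²⁰ gives 64%.

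| Correlation between markers | At least one marker selected | Mean apparent AUC if any selected | Share of all null trials reaching 0.713 |
|---|---|---|---|
| 0 | 59–65% | 0.71 | 24–25% |
| 0.3 | 47–53% | 0.70–0.71 | 17% |
| 0.5 | 38–41% | 0.70 | 11–14% |

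Further scenarios, also on pure noise:

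- **Screen at p<0.10:** 46% of all trials reach 0.713 with independent markers, and 14–30% with correlated ones.
- **Age and TNM forced in as noise, independent markers:** 38% (p<0.05 screen) or 59% (p<0.10 screen) reach 0.713.
- **All 20 entered:** median apparent AUC 0.86, with more than 99% at or above 0.713. Adding age and TNM gives a mean of about 0.88–0.89.
- **Best single marker of the 20:** reaches 0.713 in 7–12%.
- **Fixed model of LDH, NLR, age and TNM:** median 0.64, reaching 0.713 in about 12%.

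**If age and TNM were screened like the markers.** A real confounder with an assumed odds ratio of 1.5 per SD would pass p<0.05 in about 27–31% of trials. At 2.0 per SD it would pass in about 65–67%.

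**The case against.** The strongest reply is that the SAP never says 20 markers enter one model. Its 5-events rule is worded for variables that are controlled for, and it is applied to age and TNM. The reading closest to SAP section 4 is each primary marker adjusted for those two, which fits 22 events. Secondary objectives 2 and 3 speak only of exploring correlations. Only objective 4 calls for a combination, and it names no markers. No section mentions a p-value screen or says that age and TNM are subject to one.

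All of that stands, and it rules out two stronger statements that a reader might infer. The first is that the plan breaks its own rule. It does so if candidates are counted, or if all 20 enter, but not necessarily if only the terms of the final model are counted. The second is that noise will look as good as LDH is planned to look. The 0.70–0.71 is an average over trials in which something was selected. Across all null trials after a p<0.05 screen, only about 11–25% reach 0.713, and the lower figures may be the more relevant, since NLR, LMR, PLR and SII share cell counts. Noise comes nowhere near the 0.998 implied for NLR under a screen.

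What the reply does not remove is the gap itself. A compliant reading exists, but SAP section 5 does not commit to it.

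**Conclusion.** The point holds as a gap in specification. About 22 events support about 4 variables, 20 marker-days are named and the list is open, and SAP section 5 neither limits the terms nor names age and TNM. Depending on choices left open, the adjusted predictors and the combined model may be sound, may rest on about 1 event per variable, or may be partly chance selections.

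The unadjusted POD1 comparisons of drain LDH and NLR are prespecified and do not depend on any of this, so the documents do not support reading it as a threat to the primary comparison.

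The event count takes the SAP's 38% (3:5) at face value. The protocol's background puts postoperative ileus at about 10–30%. At 30%, 59 × 0.30 = 17.7 events, which supports 3 variables; at 10%, 5.9 events, which supports 1. The simulated figures also assume normal markers, the stated thresholds, correlation 0 to 0.5 and one term each for age and TNM. They are scenarios, not predictions. The same arithmetic cannot be done for the complications model, because no complication rate is given.

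This should be changed, but it does not invalidate the plan.

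**What to change.** Change SAP section 5 as follows:

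1. Close the marker list: name the 20 marker-days and drop the open-ended wording.
2. For each primary marker (POD1 drain LDH and NLR), fit marker + age + TNM as one term, with the coding of TNM stated. Force age and TNM in and use no univariate screening.
3. For secondary objective 4, prespecify one combined model of at most 4 parameters, counting any covariates. Alternatively, fit a ridge or LASSO model over the listed markers. Report an optimism-corrected AUC from a bootstrap that repeats every selection or tuning step. Fixing the terms alone is not enough, since the fixed four-term model still reached 0.713 on noise in about 12% of runs.
4. Report the other marker-days as univariable estimates with confidence intervals, labelled exploratory.

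The cost is SAP wording and some programming for the bootstrap, with no extra patients or measurements. The downside is fewer adjusted results for the secondary markers.

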## **6. Data collection and management**

Simultaneous recording of electronic data and paper report forms.

## **7. Data Management Programmer**

Paper files were sealed one at a time in the order of entry into the group, opened and recorded during interim analysis and data analysis, and stored and backed up in a timely manner. Regularly updated on [clinicaltrials.gov](https://clinicaltrials.gov).

